[figure not shown]

## **I. Background & Rationale**

Simple cold storage (CS) has been the preferred method of organ preservation for most transplant centers in Europe. Major transplant centers in the US have indicated that continuous hypothermic machine perfusion (MP) has definite advantages over CS with reduced percentages of delayed graft function (DGF) after kidney transplantation. Nevertheless, in most European centers, predominantly due to logistics and the perception of increased costs, MP has not been utilized or properly evaluated. Therefore no decision has been made as to the standard of care for organ preservation in particular how the preservation method (CS or MP) will affect outcome after transplantation. This Study proposes a prospective randomized trial within an international organ sharing system to evaluate early graft function after MP preservation versus CS preservation.

Within the Eurotransplant (ET) region results after kidney transplantation have improved due to better immunosuppression and standardized techniques. However, in part due to older and more 'marginal/extended' donors DGF rate after kidney transplantation has risen to as high as 35%; despite the 21% reduction when the University of Wisconsin Cold Storage preservation solution (UW-CS) was introduced as the standard in the late nineteen eighties. In the past, in animal experiments as well as in historical controlled clinical studies MP has been shown to provide better early graft function than when kidneys were cold stored. In addition, when kidneys from extended donors, with long preservation times, and from non-heart beating (NHB) donors were used, MP has shown to be beneficial. A review of current literature concerning data on MP vs. CS, as the method of organ preservation, revealed a 20% reduction in DGF when MP was the preservation modality. Historical data also showed that DGF in combination with acute rejection was found to be significantly associated with a 10-15% decrease in graft survival, thus requiring restart of dialysis and retransplantation in a large number of recipients. Lastly, DGF inevitably leads to dialysis, prolonged hospital stay, and increased cost in the short and long term, especially when the graft fails and costs of dialysis while on the waiting list for a second transplant is included.

As stated above, for reasons of practicality, MP was abandoned or not even introduced by many programs. It needs equipment and consumables, can be labor intensive and carries the risk of equipment failure. Therefore, its usage seemed not justified versus the simplicity and low cost of CS. However, the question of superior early graft function of donor kidneys preserved by MP vs. CS remains unresolved and the added benefit of MP use for the more difficult donor kidneys needs to be quantified. While data point at potential benefits of MP that would imply not only less DGF, but also less acute rejection, and a better short- and long-term function at reduced cost, no real comparative data of these modalities under strict conditions has been done.

In this study, we attempt to resolve the controversy and will answer the question whether or not MP is superior in preservation of cadaveric kidney grafts and logistically feasible within an international organ sharing system.

## **II. Trial Design**

A prospective randomized controlled multi center trial of paired kidneys from cadaveric donors (the "study").

## **III. Objectives/Outline of the Study**

### Main aim of the study:

Does MP with UW-MP (Kidney Preservation Solution: KPS-1) improve early graft function in cadaveric renal transplantation in comparison to UW-CS (Viaspan®)? Assuming the 0-hypothesis that MP and CS give equal early graft function, the alternative hypothesis is that early graft function improves with MP.

### Primary endpoint:

DGF, defined as any dialysis requirement within 7 days post transplant.

### Secondary endpoints:

Duration of DGF, renal function (serum creatinine; 1/creatinine; creatinine clearance; decrease of serum creatinine > 10% per day for at least 3 consecutive days for more than one week after tx; length of hospital stay; acute graft rejection, hyperkalemia, calcineurin inhibitor toxicity), graft and patient survival at 1-year.

### Additional points for evaluation (amendments):

Participating regions have the opportunity to suggest amendments to this basic study protocol. Proposed amendments will be discussed by the Steering Committee and adopted for either all regions, regionally, or rejected. Costs of accomplishing these amendments will be considered outside of the basic financial support structure of the study and are the responsibility of the proposing group.

## **IV. Study Population**

### Identification of donors

All potential consecutive cadaveric kidney donors >16 years from the collaborating donor regions (Belgium, The Netherlands and Nordrhein-Westfalen in Germany) reported to the ET desk are eligible for randomization.

This includes all heart beating organ donors and, in The Netherlands and Belgium, NHB donors (including Maastricht categories 3 and 4, excluding categories 1 and 2). No NHB donor kidneys will be procured or transplanted in Germany. Donors will meet the general and organ specific criteria for kidney donation. Donors will be managed by the local coordinator according to loco-regional and ET directions.

### Randomization of donor kidneys

After accepting the potential organ donor for actual donation, one of the kidneys is randomized to preservation by MP with the contralateral organ serving as a control being preserved by CS (ET desk has randomization scheme).

In case, due to circumstances, only one kidney is eligible for procurement, preservation and transplantation, while the contralateral kidney is discarded, the eligible kidney will be cold stored.

In case of a recipient with a multi organ transplantation (pancreas, lung, liver, heart, or small intestine plus kidney), this kidney and the contralateral kidney will be excluded from the study. When technical

problems with MP are expected and the perfusionist, according to training, cannot fix the problem, preservation methods may be switched, thus frustrating initial randomization.

To guarantee a balanced design, block randomization may be applied (at the discretion of the Central Trial Assistance (CTA) that will assure that there are 300 paired sets at the end of the study). The first 24 left kidneys will be assigned to the treatment arms according to the scheme: AABB BBAA ABAB BABA ABBA and BAAB, with A=MP and B=CS. Obviously, the right kidneys will be assigned to the other treatment arm. The sequence for the following 24 kidneys will be determined at random.

Kidneys are offered for transplantation following the ET allocation rules. Whenever one of two kidneys is not transplanted (for whatever reason) or both kidneys are preserved in the same way (i.e. CS for double multi organ transplants) transplants are excluded from analysis for this study.

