## **VII. Organ Allocation Logistics**

Organ allocation logistics, including transportation logistics to the assigned transplant center, will be, as usual, the responsibility of ET in close collaboration with the transplant coordinator. In defiance to standard procedures: to prevent possible bias during the study period, ET will at time of offering of the donor kidneys included in the study reveal all pertinent information to the recipient centers but not the preservation method before the individual center has made its appropriate choice for a left or right kidney on recipient or center related grounds. Otherwise, logistics will follow standard policies and the study should not change any procedure or the timing of transplantation in individual recipient centers.

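### The side assignments of the first 24 donors are fixed and printed with their key, so up to 8% of the planned pairs are not randomly allocated and the masking of recipient centres is weakened for them.

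*Protocol*

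**What the plan says.** Section II calls the study a randomised controlled trial of paired kidneys. Section IV (Randomization of donor kidneys) says that one kidney of each accepted donor is randomised to machine perfusion (MP) and the other is cold stored (CS), and notes "ET desk has randomization scheme".

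The same section then describes the sequence. Blocking is optional: "To guarantee a balanced design, block randomization may be applied", at the CTA's discretion. The start of the list is not worded as optional: "The first 24 left kidneys will be assigned to the treatment arms according to the scheme: AABB BBAA ABAB BABA ABBA and BAAB". The sentence also decodes the letters. The other side follows: "Obviously, the right kidneys will be assigned to the other treatment arm". Next comes "The sequence for the following 24 kidneys will be determined at random". Nothing is said about allocation after donor 48.

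Section VII departs from usual practice to limit bias. At the offer, ET gives the recipient centre all relevant information, "but not the preservation method before the individual center has made its appropriate choice for a left or right kidney". Addendum 4, Scenario 1, repeats this: the ET desk makes the offer without the method, and the recipient centre learns it only after accepting.

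**The concern.** Two properties of a randomised allocation are in question for these donors.

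- **Randomness.** The protocol itself contrasts a fixed list for the first 24 donors with a random one for the next 24. The fixed part cannot be described as randomised.
- **Concealment.** Holding the scheme at the ET desk does not hide a list printed, with its key, in the protocol. A recipient centre that knew the donor's place in the list could work out which side was perfused before choosing a side.

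If that happened, a centre could match its recipient to a method, and recipient risk would no longer be independent of treatment. It could also let the method influence whether it accepts the kidney. Section IV removes both transplants of a donor from the analysis when either kidney is not transplanted, so acceptance also affects which pairs are analysed. The primary endpoint, delayed graft function (DGF), depends on recipient factors that section XIII itself lists, so a link between recipient and method would reach the primary comparison.

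**Working it through.** **1. The denominator.** Section XIII plans 300 donors, with power 0.80 and p < 0.05. It does not say whether the test is two-sided or whether the 10% reduction is absolute. Assume 30% DGF with CS (the midpoint of the 25-35% in section XII), 20% with MP, a two-sided test and the unpaired formula with pooled variance:

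n = [1.96 × √(2 × 0.25 × 0.75) + 0.8416 × √(0.30 × 0.70 + 0.20 × 0.80)]² / 0.10²
= (1.200 + 0.512)² / 0.01 ≈ 293.2, so 294 per arm.

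This reproduces 300 to within 3%. The relative reading in section XII (RR 0.9) does not give 300; that is a separate matter and does not affect the share below.

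**2. The share.** 24 / 300 = 8.0% of planned pairs.
- Section IV excludes some pairs after allocation and still aims for 300 paired sets. With any exclusions, more than 300 donors are allocated, and some of the first 24 may drop out. For a single sequence, 8% is therefore an upper figure.
- The protocol does not say whether the three regions share one list. If each ran the scheme separately, the share would be 3 × 24 / 300 = 72 / 300 = 24%.

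**3. The structure of the list.** The six printed blocks are the six possible arrangements of AABB, each used once, giving 12 A and 12 B. They are set out as three mirror-image couples (AABB with BBAA, ABAB with BABA, ABBA with BAAB). The list is balanced for side, but its order is fixed.

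**4. Predictability.** For a reader who knows the donor's position, all 24 assignments are known. For comparison, take someone who guesses as well as possible within truly random blocks of four and sees every previous assignment. The chances of a correct guess at positions 1 to 4 are 1/2, 2/3, 2/3 and 1. The sum is 17/6 per block, so six blocks give 17 of 24 correct.

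If blocks of four were continued, which the protocol does not state, the fourth position would be forced in all six arrangements and the third in two (AABB and BBAA): 6 + 2 = 8 of 24 positions, or one third.

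**5. Who knows the method, and when.**
- *Donor side.* Under section VI and Addendum 4, ET assigns the sides once the donor is reported and calls the perfusionist at once, and the coordinator is told which kidney is perfused. This holds for every donor, so the printed list adds little there.
- *Recipient side.* The method is withheld until a side has been chosen (section VII) or the offer accepted (Addendum 4). This is the step at which foreknowledge adds something.
- *Donor selection.* All consecutive donors are eligible (section IV), and each analysed donor gives one kidney to each arm. Foreknowledge cannot unbalance donor factors between arms.

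**6. What leaving the 24 out would cost.** With the assumptions of step 1, power is Φ[(0.10 × √n − 1.200) / 0.608]. For n = 300 this is 80.9%; for n = 300 − 24 = 276 it is 77.6%.

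**The case against.** The strongest reply is that the list alone is not enough to predict an assignment. A reader also needs the donor's running number. Donors come from three regions, and the documents place the view of the whole sequence only at the ET desk. Nothing shows that recipient centres hold the protocol or learn the number, and some centres lie outside the trial regions (Addendum 4, Scenario 3). ET still withholds the method at the offer for these donors, and kidneys are offered under ET's allocation rules. All of this stands, and it limits the concealment part of the point. Perfusionists and coordinators see assignments in their own region and might infer a position, but less easily across three regions.

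Several stronger readings are tempting but unsupported:

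- *A reader might infer that anyone could tell which side would be perfused, or that the allocation was public during enrolment.* The documents do not say who holds the protocol, and the running number is still needed.
- *A reader might infer that the list lets donor teams swap methods with foreknowledge.* They know the method before procurement for every donor, and the switches that sections IV and V permit are made with it known.
- *A reader might infer that a third of later assignments are also exposed.* Blocking is discretionary, its later size is not stated, and the observer would have to see the whole sequence.
- *A reader might hold blocking itself to be an error because each pair already supplies one MP and one CS kidney.* Balancing left and right is a legitimate aim.

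The discretionary wording about blocking does not rescue the list, because the sentence on the first 24 says that it will be used. Nor do these replies answer the contradiction with the claimed randomisation.

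**Conclusion.** The point holds in a limited form. As written, the first 24 donors are allocated by a fixed, printed and decoded list, which contradicts the randomised design stated in sections II and IV. They are at most 8% of the 300 planned pairs if there is one trial-wide sequence. If each region used the list, which the protocol does not settle, they would be 24%.

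For these donors the masking in section VII is weakened, on the condition that someone at the recipient centre has the protocol and knows or infers the donor's place in the list. It would go too far to say that the masking is defeated. The exposure is mainly the recipient centre's choice of side and its acceptance of the kidney. No bias in the DGF estimate is shown, and donor factors stay balanced by the pairing. The point still deserves correction because lost randomness cannot be restored once these pairs are allocated, while prevention costs almost nothing.

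**What to change.** Delete the printed scheme and its key from section IV. Have the CTA generate the whole left/right list at random before the first donor, either by simple randomisation of side or with varying block sizes that are not disclosed. Hold the list only at the ET desk. State that the method covers all donors, including those after donor 48, and whether there is one list or one per region.

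If the 24 have already been allocated, report the primary analysis with and without them. The detail can sit in the statistical analysis plan, which is not at hand. Keeping all pairs in the main analysis preserves its power; the version without the 24 would have 77.6% instead of 80.9% under the assumptions above.

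The cost is one new list and one changed paragraph. A slight left/right imbalance is possible. The balance of MP against CS and the sample size are unaffected.

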## **VI. Machine Perfusion**

Prior to the study three Regional Perfusion Centers (RPC) (Groningen, Essen and Leuven) will be established as separate entities that are responsible for the logistics that will allow a safe and high quality procedure using machine preservation according to the state of the art and ruling quality standards. For a good conduct of this study three teams of perfusionists will be trained by professionals from ORS to take care of preservation machines, handle donor kidneys in collaboration with the donor surgeon and accompany the transport of the preservation devices as well as accumulate data for the study. Details concerning the training, responsibilities and standard operation procedures are defined in a separate logistics support protocol (see addendum 4). Each RPC will have a Regional Supervisor who is not the Principle Investigator for that region.

During the study, after reporting a donor for kidney donation, randomization by the ET desk is performed and the transplant coordinator on duty is informed which kidney should be machine perfused and which kidney cold stored. Next the Regional Perfusion Center (RPC) is notified by the transplant coordinator on duty concerning the expected donor operation and told at what point in time a MP-unit ought to be present in the OR at the donor hospital.

At the time the donor operation begins, the RPC will have arranged logistics concerning MP, e.g. the perfusion machine including cannulae, preservation solutions, questionnaires, etc. All details will be available and ready for use in the operating room at the donating center. The RPC, in close collaboration with the responsible transplant coordinator and ET will coordinate and take care of the logistics

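### Pairs are dropped after randomization whenever a kidney is not transplanted, with no exception for loss caused by the assigned preservation method

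*Protocol*

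**What the plan says.** **Timing of randomization.** Section IV (Randomization of donor kidneys) states: "After accepting the potential organ donor for actual donation, one of the kidneys is randomized to preservation by MP". Section VI agrees: "after reporting a donor for kidney donation, randomization by the ET desk is performed", and only then is the perfusion center told of the expected donor operation. Assignment therefore precedes procurement, preservation and transplantation.

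**Exclusion rule.** The last paragraph of the same part of Section IV gives two triggers. The first is "Whenever one of two kidneys is not transplanted (for whatever reason". The second is that "both kidneys are preserved in the same way (i.e. CS for double multi organ transplants) transplants are excluded from analysis for this study".

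**Related rules.** If only one kidney is usable, "while the contralateral kidney is discarded, the eligible kidney will be cold stored". If a technical problem with MP is expected and cannot be fixed, "preservation methods may be switched, thus frustrating initial randomization". Section V allows a similar switch when a vascular anomaly prevents perfusion.

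**Target.** Section IV has the Central Trial Assistance assure 300 paired sets at the end of the study. Section XIII plans 300 donors.

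**Risk and recording.** Of MP, Section I says: "It needs equipment and consumables, can be labor intensive and carries the risk of equipment failure". Section IX has adverse effects attributed to either method recorded at the donor and recipient operations. Section VI has the perfusionist collect feasibility data. The primary endpoint is dialysis within 7 days of transplantation. Neither it nor any secondary endpoint counts kidneys that were never transplanted.

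**The concern.** The exclusion depends on an event that follows randomization and that the assigned method can bring about. MP kidneys pass through steps that CS kidneys do not: cannulation, unattended travel on the device and, for recipients outside the trial region, removal by a surgeon working from an instruction sheet with no perfusionist present. A kidney lost at one of these steps takes its pair out of the analysis, and a further donor makes up the 300.

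The study asks both whether MP is superior and whether it is logistically workable. A comparison restricted to pairs in which both kidneys were transplanted answers a narrower question: how graft function compares once both organs have survived preservation. If one method loses more organs than the other, that restricted comparison flatters it. The restriction is fixed in the protocol's definition of the analysis set, so it is not a detail left to an analysis plan.

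**Working it through.** **1. The plan's own figure.** Inputs: CS DGF of 25-35% (Section XII; midpoint 30% assumed), a 10% reduction read as 10 points, power 0.80 and p < 0.05 (Section XIII; two-sided assumed). With pooled variance and no continuity correction:

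n = [1.96 × √(2 × 0.25 × 0.75) + 0.8416 × √(0.30 × 0.70 + 0.20 × 0.80)]² / 0.10² = 293.2, so 294 per arm.

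This reproduces the planned 300 closely. Power at 300 per arm is 0.81. The figure contains no allowance for lost pairs. The working case below is therefore 30% against 20%, or 90 against 60 events in 300 complete pairs.

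**2. Kidneys lost in MP only.** The documents give no loss rate, so k = 3, 6 and 12 (about 1-4% of 300) are assumptions. Since the trial fills to 300 complete pairs, k lost MP kidneys mean 300 + k randomized pairs. Keep the k transplanted CS partners at 30% DGF and count each lost MP kidney as a failure. The MP rate is then (60 + k)/(300 + k).

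| k | MP failures | MP rate | Difference from 30% |
|---|---|---|---|
| 0 | 60/300 | 20.0% | 10.0 points |
| 3 | 63/303 | 20.8% | 9.2 points |
| 6 | 66/306 | 21.6% | 8.4 points |
| 12 | 72/312 | 23.1% | 6.9 points |

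The plan as written shows the first row whatever k is.

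**3. Kidneys that revert to ice and are transplanted.** These are not lost organs. If all 12 revert and have DGF at the CS rate, MP is (60 + 0.30 × 12)/312 = 63.6/312 = 20.4%, a difference of 9.6 points.

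**4. Symmetry.** If instead 12 kidneys are lost in CS only, CS is (90 + 12)/312 = 32.7% against 20% in MP, a difference of 12.7 points. Here the exclusion would understate the advantage of MP.

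**5. Effect on power if losses are counted.** With MP loss of 2% (close to the six-kidney row), the MP failure rate is 0.02 + 0.98 × 0.20 = 21.6%. Power at 300 per arm, treating the arms as independent, falls from 0.81 to 0.65. At 5% loss the rate is 24.0% and power is 0.38.

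**6. Whether the forms could recover the information.** Addendum 1 has one preservation-modality entry per kidney. It has no separate entry for the assigned method, and no field for why a kidney was discarded or why a device failed. In Addendum 3, preservation appears as a cause of graft failure, which applies only after transplantation.

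**The case against.** Several stronger readings are tempting, and the documents do not support them.

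- **That MP failures disappear altogether.** They do not. Adverse effects and feasibility data are recorded, and Addendum 1 captures vascular, ureteral and parenchymal damage for each kidney. What is missing is any tie from these records to a comparison by assigned arm.
- **That the bias must favor MP.** The rule also drops pairs whose CS kidney is lost, as step 4 shows. Safeguards exist too: perfusion and laboratory readings may not alter the decision to transplant, and the method is withheld until the offer is accepted. These close some routes to differential discard, but not cannulation damage, device failure or transport failure.
- **That return to ice is a stated ground for exclusion.** The only case named under the second trigger is double multi-organ transplantation, and Section VI says kidneys stay on the device until delivery. The wording could nevertheless be applied to a pair whose MP kidney reverted, so it needs narrowing.
- **That every foreseen MP problem removes the pair.** Expected technical problems and vascular anomalies may lead to a switch between the two kidneys. Such a pair still has one kidney in each method and stays in. That is a separate issue.
- **That the protocol treats equipment failure as the chief drawback of MP.** Section I lists it beside consumables and labor without ranking them.
- **That false positives are sharply inflated.** One can construct this. Suppose total failures are truly 30% in each arm and every lost MP kidney would have counted as a failure. Losses of 2%, 5% and 10% then give roughly a 6%, 17% and 58% chance of a significant result for MP, against a nominal 2.5%. That is a worst case on assumed rates, not a forecast.

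It is also fair to say that DGF is defined only after transplantation, so counting discarded kidneys as failures creates a different, composite outcome. That stands. It is why the composite belongs in a sensitivity analysis and the primary definition should be left alone.

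**Conclusion.** The concern holds in a limited form. The protocol conditions its analysis set on a post-randomization event that the assigned method can cause, makes no exception for such cases, and replaces the lost pairs. Preservation-related organ loss is therefore absent from the comparative result.

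On 30% against 20% DGF, with 3 to 12 kidneys lost in MP only and counted as failures, the 10-point difference shrinks to between 9.2 and 6.9 points. The 6.9 requires all 12 to be destroyed organs with no loss in CS, so it is an upper bound on the change for that count. Twelve reverted but transplanted kidneys would leave about 9.6 points. Neither the loss rate nor the direction of bias can be established from the documents, which is itself the reason to account for losses by arm.

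**What to change.** 1. In Section IV, limit exclusions to reasons that cannot depend on the arm: donation not proceeding, a kidney ineligible before preservation starts, or a multi-organ recipient.
2. Restrict the second trigger to the multi-organ case, and analyze other transplanted pairs as assigned.
3. Report non-transplantation and device failure, with reasons, by assigned arm over all randomized pairs.
4. Add one sensitivity analysis that keeps the transplanted kidney of a half-pair and counts preservation-related non-transplantation as failure. The donor frailty term in Section XIII could accommodate half-pairs. The DGF definition stays unchanged for the primary analysis.
5. Add the assigned method and the discard or failure reason to Addendum 1.

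The cost is revised wording, a little more data entry and one further analysis. The downside is a possibly smaller MP effect. The form change matters most, because reasons for loss that are not collected at the time cannot be reliably recovered later.
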